11.16.2. Interventional Pain Procedures

No interventional pain procedures to treat the SCS-targeted pain are allowed through the 3-Month Visit. Procedures associated with the SCS device (e.g. IPG Revision, Lead revision, CSF leak interventions and interventions associated with SCS procedure related adverse event management) are allowed. Excluded procedures include, but are not limited to, the following:

- Epidural steroid injection
- Facet joint injection
- Selective nerve root block
- Radiofrequency ablation
- Spine surgery (e.g., discectomy, vetebroplasty, fusion)

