7.1. Primary Endpoint

The primary endpoint is the proportion of subjects with 50% or greater reduction from the Baseline Visit in average overall pain intensity at 3 months post activation, with no increase in baseline average daily opioid medications used to treat pain.

[REDACTED]

[REDACTED]

[REDACTED]

[REDACTED]

[Redacted text block]

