10.1. Point of Enrollment

A subject will be considered enrolled in the study when the Informed Consent Form (ICF) is signed. All enrolled and activated subjects will be included in the study analyses.

If device implantation is unsuccessful, the subject will be followed for 2 weeks post implantation attempt to assess for procedure related adverse events.

10.2. *Withdrawal*

All subjects enrolled in the clinical study (including those withdrawn from the clinical study or lost to follow-up) shall be accounted for and documented. If a subject withdraws from the clinical investigation, the reason(s) shall be reported. If such withdrawal is due to problems related to investigational device safety or performance, the investigator shall ask for the subject's permission to follow his/her status/condition outside of the clinical study.

While study withdrawal is discouraged, subjects may withdraw from the study at any time, with or without reason and without prejudice to further treatment. In all cases of withdrawal or discontinuation, the Investigator will make all reasonable efforts to determine the reason for the subject's withdrawal. Subjects may be discontinued from the study for the various reasons, such as:

- Withdrawal of consent
- A safety concern defined by the Principal Investigator and/or Boston Scientific Neuromodulation (e.g., adverse event)
- Study non-compliance
- Inadequate use of device that may impact study outcomes Subject did not meet inclusion criteria or met an exclusion criterion after signing informed consent
- Surgical intervention that affects the Implantable Pulse Generator (IPG) and/or leads
- Lost to follow-up
- Death of the subject

A subject is considered lost-to-follow-up after 3 unsuccessful contact attempts have been made to reach the subject (including those who relocate but cannot be transferred to another participating site). Staff at the participating site should make a good faith effort to contact the subject with three documented communication attempts, at least one of which must be in writing, sent via a traceable method to inform the subject that the device must programmed per standard of care with commercially approved settings.

Data collected up to the point of subject withdrawal or lost to follow-up may be used for study analysis in accordance with applicable regulations.

Withdrawn subjects will be followed per the End of Study Action Plan as described in Section 10.5.

10.3. *Subject Status and Classification*

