12.1. Endpoints

12.1.1. Primary Endpoint

The primary endpoint for this study is the proportion of subjects with 50% or greater reduction from Baseline Visit in average overall pain intensity at 3 months post activation with no increase in baseline average opioid medications used to treat pain.

[Redacted text block]

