12.1.1.1. Hypotheses

The primary statistical hypothesis in this study is that the proportion of subjects with 50% or greater reduction from Baseline Visit in average daily overall pain intensity at 3 months post activation is non-inferior to an Objective Performance Criteria (OPC) of 40%.

$$H_0: \pi_{opc} - \pi_t \geq 0.20$$

$$H_1: \pi_{opc} - \pi_t < 0.20$$

Where π_t is the proportion of subjects with 50% or greater reduction from Baseline in average daily overall pain intensity at 3 months post activation with no increase in baseline average daily opioid pain medications using Spectra WaveWriter. π_{opc} is the responder rate of an OPC based on Kumar paper (Kumar 2008).

[Redacted text block]

- **Safety Population:** All subjects who sign the IRB-approved written Informed Consent form

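### On its visible wording, the primary endpoint does not score a prohibited interventional pain procedure as a failure, so relief after one can count as a response to the device

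*Combined protocol and SAP*

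**What the plan says.** **The prohibition.** Section 11.16.2: "No interventional pain procedures to treat the SCS-targeted pain are allowed through the 3-Month Visit". The list that follows is open-ended ("Excluded procedures include, but are not limited to, the following") and names epidural steroid and facet joint injections, selective nerve root block, radiofrequency ablation and spine surgery. Procedures connected with the stimulator itself, such as lead or generator revision, are permitted.

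**The endpoint.** Section 7.1 requires a reduction of at least 50% from the Baseline Visit "at 3 months post activation, with no increase in baseline average daily opioid medications used to treat pain". The synopsis and Section 8.2 match it. Section 12.1.1 repeats both conditions: "at 3 months post activation with no increase in baseline average opioid medications used to treat pain". In Section 12.1.1.1, π_t carries the same pair, the second being "post activation with no increase in baseline average daily opioid pain medications using Spectra WaveWriter". The synopsis version of π_t refers to pain medications rather than opioids. None of these mentions an interventional procedure.

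**Who is analysed.** Section 10.1: "All enrolled and activated subjects will be included in the study analyses". Section 10.2 lists non-compliance as a possible reason for discontinuation, but does not make discontinuation mandatory. Section 15 requires deviations to be documented and reported, and attaches no visible consequence for the analysis.

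**The test.** Section 12.1.1.1 tests whether the responder proportion "is non-inferior to an Objective Performance Criteria (OPC) of 40" per cent, with a margin of 0.20.

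**The concern.** The protocol prohibits two things that could lower the 3-month pain score without help from the stimulator: changes to opioids (Sections 11.3 and 11.17) and interventional procedures for the same pain (11.16.2). It treats them differently in the endpoint. An opioid increase is already a deviation, yet the endpoint also makes it a failure, so for opioids the plan does not rely on the prohibition alone. For procedures prohibited up to the same visit, the visible endpoint has no such safeguard.

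The neighbouring section shows that the plan does consider this kind of event. Section 11.16.1 says that effectiveness data from subjects who agree to a revision stay in the intent-to-treat analysis. Section 11.16.2 is silent on how subjects with a prohibited procedure are analysed.

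What is at stake is attribution. The design is open-label and single-arm and is compared with a fixed performance criterion, so no control group carries the same rescue effect. A subject whom the device failed, and who was then relieved by an ablation, would be evidence for the device.

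**Working it through.** **1. Apply the visible definition to one case.** A subject is activated, gets inadequate relief from stimulation, has a prohibited radiofrequency ablation, keeps opioids unchanged, and reports a 60% reduction at 3 months.
- Reduction of at least 50%: met.
- No opioid increase: met.
- Further visible condition: none.
- Kept in the analyses (10.1): yes, unless discontinued at discretion (10.2).

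Result: responder.

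**2. Direction.** Compared with scoring such subjects as failures, the visible rule can add responders but never remove them. The bias is upward.

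**3. Exclusion is not a cure.** Suppose those who have a procedure are all device failures and are dropped. At a true 20%, dropping 3% gives 0.20 / 0.97 = 20.6%; dropping 10% gives 0.20 / 0.90 = 22.2%. The 3% and 10% are assumptions.

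**4. Illustrative size.** The plan shows no figure to reproduce: sample size, alpha and the assumed responder rate are not visible.
- From the plan: criterion 0.40, margin 0.20, so the null boundary is 0.40 − 0.20 = 0.20.
- Assumed: n = 75; exact binomial test at one-sided 0.025; 3% to 10% of activated subjects have a prohibited procedure; half of them then become responders; every one of those would otherwise have failed.
- Added responders: 0.03 × 0.5 = 1.5 points; 0.10 × 0.5 = 5 points.
- Success requires the smallest r with P(X ≥ r | 75, 0.20) ≤ 0.025. This is r = 23.

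| True device rate | Nothing added | +1.5 points | +5 points |
|---|---|---|---|
| 20% (null boundary) | 0.019 | 0.041 | 0.158 |
| 40% (equal to the criterion) | 0.963 | 0.980 | 0.996 |

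The upper case at the boundary (25% observed) depends on n: 0.098 at n = 50, 0.208 at n = 100 and 0.282 at n = 150.

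**5. Can the event be identified?** The Resource Utilization Inventory (13.2.16) lists non-surgical procedures only. Procedure Information (13.2.11) covers stimulator procedures only. A prohibited spine surgery would have to be found through deviation, unscheduled-visit or adverse-event records.

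**6. Relevant window.** Reduction is measured from the Baseline Visit. Implant may take up to 90 days after that visit (11.6) and healing up to 28 days (11.7), both before activation. A procedure in that interval could lower the 3-month score just as one after activation could.

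**The case against.** The strongest objection is redaction. Redacted text follows 7.1, 12.1.1 and the hypotheses. Of the analysis sets only the Safety Population is visible, and most of 12.3 is withheld. Responder derivations, deviation handling or a per-protocol set would normally sit there, and redacted text is not missing from the plan. A reader might infer that the trial does count such subjects as responders. The documents do not support that: a non-responder rule may already exist. What can be said is that they meet the visible definition.

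Two further inferences also go too far. Section 10.1 decides who is included, not how a subject is scored, so it does not settle the outcome by itself. And Section 11.16.2 gives no reason for its prohibition, so one cannot say that the protocol itself regards these procedures as confounders.

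On size, every input except the 20% boundary is assumed. Nothing visible suggests that prohibited procedures would be common in this period, and treating every added responder as an otherwise certain failure makes the result an upper bound for the chosen frequencies. If the device performs at the 40% criterion, the result hardly changes.

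All of this limits the claim. It does not remove the gap in the visible wording, which is the same in every place where the endpoint is defined.

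**Conclusion.** The point holds in conditional form. No visible endpoint text makes a prohibited procedure a failure, and on that text relief following one is credited to the stimulator. The direction is upward and no control arm offsets it. The amount is unknown because the documents give no procedure frequency. Under the stated assumptions it matters when the true rate is near the 20% boundary, where even the low case roughly doubles the chance of a false success (0.019 to 0.041), and very little when the true rate is near 40%. It should be corrected or confirmed because the remedy is cheap and the plan already applies the same logic to opioids. It does not show that the trial's conclusion would be wrong. If the redacted text already scores these subjects as non-responders, confirmation from the sponsor closes the point; a rule that only excludes them would not close it if most are device failures.

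**What to change.** First, the sponsor should confirm whether the redacted analysis text already scores these subjects as non-responders. If it does not:

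- Add to the endpoint in 7.1 and 12.1.1, and to π_t in 12.1.1.1 (with the synopsis and 8.2 aligned), that a subject who receives a procedure excluded under 11.16.2 for the SCS-targeted pain, between the Baseline Visit and the 3-Month pain assessment, is a non-responder in the primary analysis whatever the pain score.
- State that the device-related procedures permitted by 11.16.2 do not trigger this rule.
- Report the responder rate without the rule as a sensitivity analysis.
- Add one eCRF item at the 3-Month Visit recording any such procedure and its date, since the existing forms would not reliably capture spine surgery.

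This changes scoring only, not patient management. The cost is a sentence in each endpoint definition, one derived variable, one eCRF item, and possibly a slightly lower responder rate.

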11.17. Medication Requirements

Opioid Medication Lock Period (Medication Lock visit to 3-Month Visit):

Investigators/Subjects will not be allowed to change opioid pain medications from the Medication Lock visit until completion of the 3-Month Visit. Type/dose/route must remain unchanged.

The use of acute opioid pain medication for procedural discomfort is allowed during the Procedures and Healing Period and in the event of the revision or replacement of leads, extensions and/or IPG, per site’s routine care.

Opioid Medication Open Period (3-Month Visit to End of Study visit)

Investigators/Subjects may change opioid pain medications during the pain medication open period, from the 3-Month Visit to the 1-Year, End of Study Visit as needed.

11.18. Study Completion

All activated subjects permanently implanted will be followed through completion of the 1-Year Visit or study withdrawal. The End of Study Action Plan (see Section 10.5) defines the actions to be taken when the subject reaches the end of their study participation.

11.19. Source Documents

Table 11.17-1 summarizes all source data requirements for this study. Any information first captured on an electronic data collection platform or within the EDC system on eCRF evaluations, assessments or questionnaires, not initially documented in another record, is considered the source documentation.

Table 11.17-1: Source Documentation Requirements

| Requirement | Disposition |
|---|---|
| Hospital records and/or clinical and office charts including the evidence of but not limited to inclusion/exclusion criteria, informed consent, procedures, exams, SCS System procedure(s) and devices used, evaluations, health economic assessments, laboratory results, medications, assessment of adverse events. | Retained at investigational site |
| Assessments and questionnaires | Retained at investigational site and/or electronic data collection platform/EDC |
| Programming information | Retained at investigational site and/or electronic data collection platform/EDC |
| Imaging films/prints documenting lead(s) location | Retained at investigational site |

12. Statistical Considerations

12.1. Endpoints

12.1.1. Primary Endpoint

The primary endpoint for this study is the proportion of subjects with 50% or greater reduction from Baseline Visit in average overall pain intensity at 3 months post activation with no increase in baseline average opioid medications used to treat pain.

[Redacted text block]

12.1.1.1. Hypotheses

The primary statistical hypothesis in this study is that the proportion of subjects with 50% or greater reduction from Baseline Visit in average daily overall pain intensity at 3 months post activation is non-inferior to an Objective Performance Criteria (OPC) of 40%.

$$H_0: \pi_{opc} - \pi_t \geq 0.20$$

$$H_1: \pi_{opc} - \pi_t < 0.20$$

Where π_t is the proportion of subjects with 50% or greater reduction from Baseline in average daily overall pain intensity at 3 months post activation with no increase in baseline average daily opioid pain medications using Spectra WaveWriter. π_{opc} is the responder rate of an OPC based on Kumar paper (Kumar 2008).

[Redacted text block]

- **Safety Population:** All subjects who sign the IRB-approved written Informed Consent form

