7.5. Primary Safety Parameters

[figure not shown]
Safety parameters include the rates of occurrence of all device and procedure related non-serious adverse events, all serious adverse events, and unanticipated adverse events through the end of the study.

8. Study Design

The study is a prospective, multi-center, single-arm open-label study with an adaptive design. All participants will receive the Spectra WaveWriter Spinal Cord Stimulator (SCS) system and followed per the study schedule as shown in study schematic Figure 8.1-1.

[Redacted text block]

Figure 8.1-1: VERITAS Study Design

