9.2. Inclusion Criteria

Subjects who meet all of the following criteria (see Table 9.2-1) may be given consideration for inclusion in this clinical investigation, provided no exclusion criterion (see Section 9.3) is met.

Table 9.2-1: Inclusion Criteria

| | |
|---|---|
| 
Clinical Inclusion Criteria
 | 
IC1. Chronic pain of the trunk and/or limbs for at least 6 months [REDACTED]
 
IC3. Average overall pain intensity (leg and/or low back pain) of 6 or greater on a 0-10 numerical rating scale at Baseline Visit based on 7-day recall [REDACTED]
 
IC6. Willing and able to comply with all protocol-required procedures and assessments/evaluations [REDACTED]
 
IC8. 22 years of age or older when written informed consent is obtained [REDACTED]
 
IC10. Able to independently read and complete all questionnaires and assessments provided in English
 |
|---|---|

| | |
|--|--|
| | 
IC11. If female of childbearing potential: not pregnant, as evidenced by a negative pregnancy test at Screening
 
IC12. Subject signed a valid, IRB-approved informed consent form (ICF) provided in English
 |
|--|--|

Abbreviations: Spinal Cord Stimulation (SCS), Directions for Use (DFU), Milligram (mg), Institutional Review Board (IRB), Informed Consent Form (ICF)

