Subjects who provide written informed consent but do not meet all of the study eligibility criteria will not be implanted or activated. These subjects will be deemed as "enrolled but not activated" and their reason for ineligibility will be documented.

Enrolled subjects who are not activated will not count towards the enrollment cap. Subjects who sign consent, meet all eligibility criteria, undergo permanent implant and are activated cannot be replaced.

[REDACTED]

[REDACTED]

[REDACTED]

10.5. *End-of-Study Action Plan*

When each subject completes the 1-Year Visit or withdraws, the subject exits the study and ends study participation. Subjects may continue to use their system per the applicable Directions for Use and will be followed according to standard of care.

If the study is terminated early due to sponsor discretion or due to the discovery of an unexpected, significant, or unacceptable risk/safety concern regardless of how far along the subject has reached in their study follow-up, subjects will be followed according to standard of care. Sites will have 30 days to notify all subjects of study closure.

If device implantation is unsuccessful, the subject will be followed for 2 weeks post implantation attempt to assess for procedure related adverse events. If the device is explanted, the subject will be followed for 30 days post explant to assess for related adverse events.

Device related adverse events and/or deficiencies occurring after study participation, withdrawal from the study, or after the specified timeframe following unsuccessful trials, implant failures, and explants, should be reported to BSN Patient Care at: [contact]. Such complications should not be captured as adverse events in the study.

11. Study Methods

11.1. *Data Collection*

There are a number of different study assessments required at each visit. The data collection schedule is provided in Table 11-1. Full descriptions for all assessments are provided in Section 13.

Table 11.1-1: Data Collection Schedule

| | Screening | Opioid Medication Lock Visit | Baseline Period | Baseline Visit | Implant Procedures (Trial and Permanent) | Activation Visit | Programming Period | Programming Lock Visit | Evaluation Period | 3-Month Visit | 6-Month Visit | 9-Month Visit | 1-Year Visit | Unscheduled Visit |

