11.2.2. Screening Period

Subjects undergo screening related procedures to determine eligibility for the study. It may take up to the end of Baseline Period to complete all eligibility requirements.

All enrolled subjects who are women of child-bearing potential must undergo a pregnancy test at screening. Women with positive pregnancy test results will be withdrawn from the study. The results of the test result must be documented in the subject's medical chart.

Subjects taking prescription opioids for primary chronic pain complaint (low back and/or leg pain), whose pain medications are not stable for 30 days prior to informed consent, will be withdrawn. However these subjects may be re-consented/rescreened once 30 days have passed since the last change.

Any adverse event occurring after the subject is enrolled (i.e. signing the Informed Consent Form) will be documented.

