11.5. Baseline Visit (0 – 7 days post Baseline Period)

At the Baseline Visit, subjects will return to the clinic to complete all screening requirements. Any adverse since the last study visit will be collected.

The following assessments, as outlined in Table 11.1-1, will be conducted:

- Demographics
- Medical history
- Beck Depression Inventory (BDI-II)
- Oswestry Disability Index (ODIv2.1a)
- Short Form Health Survey 36 (SF-36v2)
- EQ-5D 5-Level
- Resource Utilization Inventory (RUI)
- Work Productivity (WPAI-SHP v2.0)
- Pain Intensity: VRS
- Pain Intensity: NRS

Subjects that meet all study criteria will be scheduled for the device implant procedures (trial and permanent implant of the SCS system). If a subject fails to meet all the eligibility criteria, they will be withdrawn from the study.

End of Visit Information:

- Subjects should be reminded not to make any changes to their opioid medications.

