13.2. Study Assessments

13.2.1. Adverse Events

Adverse event evaluation will be conducted to identify adverse events occurring during the study and classify them in regards to seriousness, relationship to the implant procedure and/or device, action taken and outcome. Safety events will be reported as specified in Table 20.4-1.

All device and procedure related non-serious adverse events, all serious adverse events, and unanticipated adverse events will be collected from the time of consent through the end of the study.

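### If per-subject device- and procedure-related event rates use the consent-based Safety Population, subjects never trialed or implanted dilute them; exposure-based denominators are a cheap improvement

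*Combined protocol and SAP*

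**What the plan says.** The Safety Population is defined as "All subjects who sign the IRB-approved written Informed Consent form". In the public text this bullet follows a redacted block after 12.1.1.1; by the table of contents it belongs to 12.2.1, Analysis Sets. It carries no exposure condition.

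Section 7.5 states: "Safety parameters include the rates of occurrence of all device and procedure related non-serious adverse events". It adds all serious and unanticipated events, through the end of the study, and names no denominator.

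The study flow separates consent from exposure:

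- Enrollment is at signature of consent (10.1). On eligibility, 11.2.2 says: "It may take up to the end of Baseline Period to complete all eligibility requirements".
- IC3 (9.2) asks for average overall pain "of 6 or greater on a 0-10 numerical rating scale at Baseline Visit based on 7-day recall", so it cannot be settled earlier.
- At the Baseline Visit (11.5): "If a subject fails to meet all the eligibility criteria, they will be withdrawn from the study". Only those who meet every criterion are scheduled for the trial and permanent implant.
- Section 10.3 confirms: "Subjects who provide written informed consent but do not meet all of the study eligibility criteria will not be implanted or activated".

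Section 13.2.1 collects reportable events from consent onward and classifies them by "relationship to the implant procedure and/or device". Section 20.3 asks more broadly about relation to the study device and study procedure, and Table 20.3-1 places cases that cannot be assessed in the possibly related class. Section 10.1 also says that enrolled and activated subjects enter the study analyses, which describes a different group from all who consent.

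**The concern.** A rate of device- or procedure-related events is read as the risk to a patient who has the procedure or receives the device. A subject who is withdrawn at the Baseline Visit had neither. Counting that subject adds one to the denominator and, with rare exceptions, nothing to the numerator. The reported rate then depends partly on how many consented subjects failed screening, which says nothing about the device. The error runs in the favorable direction, and a single-arm study has no concurrent group in which the same dilution would cancel. Upper confidence limits fall by about the same factor, so the data would also appear to rule out higher risks than they do.

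**Working it through.** **Inputs.** The visible text gives no sample size, screen-failure rate or safety event rate, so there is no figure of the plan's own to reproduce. The exposed fractions (90%, 70%, 50%), the 10% event rate and the 100 consented subjects are all assumptions.

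**Formula.** Let f = exposed/consented, r = the related-event rate per exposed subject, and u = the rate of events judged related among unexposed subjects. Then

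rate per consented subject = f × r + (1 − f) × u.

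If u is zero, this is f × r, and the relative understatement is 1 − f. Because 20.3 allows u to be slightly above zero, the factor f is approximate.

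**Point estimates** (u = 0, r = 10%):

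- f = 0.9: 0.9 × 10% = 9%, which is 10% too low in relative terms.
- f = 0.7: 0.7 × 10% = 7%, which is 30% too low.
- f = 0.5: 0.5 × 10% = 5%, which is 50% too low.

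**Exact (Clopper-Pearson) 95% intervals**, 100 consented:

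| f | By exposure | By consent | Ratio of upper limits |
|---|---|---|---|
| 0.9 | 9/90 = 10.0% (4.7 to 18.1) | 9/100 = 9.0% (4.2 to 16.4) | 0.904 |
| 0.7 | 7/70 = 10.0% (4.1 to 19.5) | 7/100 = 7.0% (2.9 to 13.9) | 0.712 |
| 0.5 | 5/50 = 10.0% (3.3 to 21.8) | 5/100 = 5.0% (1.6 to 11.3) | 0.517 |

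The upper limits shrink by close to f, but not exactly by f.

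**No events observed.** The one-sided 95% upper limit is 1 − 0.05^(1/n). For n = 90, 70 and 50 it is 3.3%, 4.2% and 5.8%, against 3.0% for n = 100.

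**Which exposure counts.** A rate per permanently implanted subject would be diluted further, because a successful trial is a second gate (8.1.1, 11.6). The denominators proposed here count exposure at the trial, so the relevant f is the fraction who began a trial or implant procedure, had a component placed, or received stimulation. The second gate is therefore not added to these figures.

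**The case against.** **No denominator is visible.** Section 7.5 names none, and the link to the Safety Population is inferred from the set's name. The text around that bullet and most of 12.3 are redacted. A reader might infer that the plan does divide related events by all consented subjects, or that it lacks an exposure-based set. The documents support neither inference, because text that is blacked out is not missing from the plan. Section 10.1, which names enrolled and activated subjects, also weakens the inference. This objection stands, and it makes the point conditional.

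**Unexposed subjects can have related events.** A reader might infer that a subject with no trial or implant cannot have a related event, so that exposure denominators lose nothing. That is too strong. Section 20.3 refers to the study procedure, which need not mean only the implant; an event tied to a step before it, such as the Opioid Medication Lock Visit, could be judged related in a subject who later fails eligibility. Table 20.3-1 also counts unassessable cases as possibly related. This objection stands: such events are probably few, but they must be kept in view.

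**The consequence is small.** There is no visible safety hypothesis or pass/fail rule, and rates per procedure or per device-exposed person-time would not be diluted. Reasons for non-implantation are recorded in EDC (12.2.2), so exposure-based rates could be produced at reporting in any case. This limits the weight of the point. It does not remove the case for fixing the denominator in advance.

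**Conclusion.** The point holds in conditional form, as an optional improvement. The design places never-trialed subjects in the only visible safety set. If per-subject related-event rates are summarized on that set, implant-procedure- and device-related rates are understated by about the factor exposed/consented: a 10% rate would show as 9%, 7% or 5% at assumed exposed fractions of 90%, 70% or 50%. The actual size cannot be derived from the documents.

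The conclusion rests on two assumptions: that the redacted text sets no other denominator, and that few or no events are judged related in unexposed subjects. It should not be read as a threat to the primary endpoint or to any decision rule, since nothing visible connects them. For all-cause serious events the consented set remains suitable, because those are collected from consent.

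**What to change.** In 12.2.1 or the safety analysis section, unless the redacted text already does so:

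- Keep the all-consented set for listings, all-cause serious events, and any event judged related in a subject with no trial or implant procedure.
- In addition, report implant-procedure-related rates among subjects in whom a trial or permanent implant procedure was begun. This retains subjects with an unsuccessful implant procedure, whom 11.6 follows for procedure-related events.
- Report hardware-related rates among subjects with any device component placed, and stimulation-related rates among subjects who received stimulation, at the trial or after activation.
- List separately every related event that falls outside these denominators, so that none is lost.
- Reconcile the 10.1 statement on enrolled and activated subjects with the Safety Population definition.

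The cost is a few sentences and no new data collection. Procedure information and programming parameters are scheduled from the Implant Procedures column of Table 11.1-1, reasons for non-implantation are in EDC (12.2.2), and 20.3 already splits device-related events into hardware and stimulation. The downside is that related-event rates will be somewhat higher, intervals wider because n is smaller, and more than one denominator must be shown.
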